7.1.1 PRODUCT DEFINITION

Product Name: scAAVrh74.tMCK.hSGCA

Gene Insert: Human alpha-sarcoglycan cDNA

Control Elements: triple E box mouse MCK promoter

AAV Serotype: rh74

7.2 STUDY DESIGN

Eligibility for subjects 7 years and older will be established by SGCA mutations, ability to cooperate for testing, willingness to practice contraception during the study (if appropriate), negative pregnancy test (for females, if appropriate), and no evidence of cardiomyopathy. HIV infection, hepatitis B, or C, or known autoimmune diseases are exclusion criteria.

IRB approved consent (18yrs. of age and older) and assent (ages 12 years up to 18 years old) forms will be obtained by the Principal Investigator ██████████ or Co-investigators and signed by parents and subjects. Pre-gene transfer immune studies include serum binding antibodies to

AAV and ELISpot assays for both AAV capsid and α -SG proteins. [REDACTED]

[REDACTED]

[REDACTED]

[REDACTED] This will be a vascular delivery trial through the femoral artery of a single leg (cohort 1A) and both lower extremities (cohorts 1B and 2) using scAAVrh74.tMCK.hSGCA. This will be a dose escalation study of scAAVrh74.tMCK.hSGCA delivered through the femoral artery to an isolated limb to maximize limb vector exposure. Three cohorts of LGMD2D subjects will be included. The lower limb muscles will be targeted to demonstrate increased muscle strength with the intent of promoting extended independent ambulation. Subjects in Cohort 1A will receive a dose of 1×10^{12} vg/kg per limb (Ideal weight to height). This first subject will receive a perfusion to a single lower extremity with a total dose of 1×10^{12} vg/kg. If safety is achieved, three subjects in Cohort 1B will receive the same dose per limb delivered to both lower extremities for a total dose of 2×10^{12} vg/kg. Subjects in Cohort 2 (n=3) will receive 6×10^{12} vg/kg total dose – split between the 2 extremities (3×10^{12} vg/kg per limb) delivered to the whole limb muscles according to the same protocol. Subjects will be appropriately sedated for the procedure with the assistance of an anesthesiologist. A detailed description of the infusion procedure is described in section 6.3 of this protocol. The goal for this study is to have efficient gene transfer, muscle fiber transduction, and gene expression levels sufficient to produce clinically meaningful results (improved ambulation= distance walked on 6MWT).

7.3 DOSE SELECTION

There will be three cohorts of LGMD2D subjects [Cohorts 1A (n=1), 1B (n=3), and 2 (n=3)] with dosing permitted by toxicology- biodistribution study and predicted by pre-clinical studies in non-human primates. The trial will start with low dose gene transfer (1×10^{12} vg/kg per limb); the first patient (Cohort 1A) enrolled will receive a single unilateral infusion to one lower extremity. The same dose will be delivered to three subjects (Cohort 1B) infused to both lower extremities. The total vector genomes dosed for each subject will be adjusted by rounding to the closest 5 kg per the discretion of the PI or designated co-investigator. The subjects in Cohort 2 (n=3) will receive a total dose of 3×10^{12} vg/kg per limb delivered to both extremities. Table 6.3 below shows dosing for the clinical trial based on weights from clinic subjects eligible for the clinical gene transfer trial.

Patient wt (kg):		20-29	30-39	40-49	50 - 59	60 - 69	70 - 79	80 - 89	90 - 99	100 - 109	110 - 119	120 - 129
Cohort	Dose/quad	Total Dose / Patient (total vector genomes)										
(1)	LD 1e12vg/kg/limb	4e13	6e13	8e13	1.0e14	1.2e14	1.4e14	1.6e14	1.8e14	2.0e14	2.2e14	2.4e14
(2)	HD 3e12vg/kg/limb	1.2e14	1.8e14	2.4e14	3.0e14	3.6e14	4.2e14	4.8e14	5.4e14	6e14	6.6e14	7.2e14

Reference Table: Total Dose (vg) per subject based on bodyweight (kg)

* LD = low dose; HD = high dose

If safety data is obtained at low dose, the third cohort of three additional subjects will receive the next escalating dose (6×10^{12} vg/kg total dose) split between the two limbs.

Subjects within a cohort will be entered at intervals of approximately 4-6 weeks. Additional time will be allowed to review the biopsy results of the first subject in the first cohort prior to

dose escalation to the next cohort. Intervals within subjects in the second cohort can be reduced base on safety observed in first cohort.

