6.3 PROTOCOL FOR GENE TRANSFER

The clinical trial is a dose escalation study of scAAVrh74.tMCK.hSGCA delivered by isolated limb infusion via a sidearm sheath (REF CP-08403; Manufacturer: Arrow) placed percutaneously in the femoral artery and allowed to circulate through the limb vasculature. Prior to vector delivery the limb circulation is isolated from the central circulation by the careful placement of occlusive balloon catheters (Tyshak II Balloon Dilatation Catheter; Manufacturer: B. Braun Intervention Systems Inc., and NuMED, Inc.) one placed through the arterial sheath in a cephalad direction positioned above the profunda artery and a second occlusive balloon positioned via a similarly placed sidearm sheath placed in the femoral vein. Following placement of the arterial and venous sidearm sheaths and before the insertion of the occlusive balloons the subject is anticoagulated with unfractionated heparin. The balloons are then positioned under flouroscopy guidance and inflated to create stasis in the limb during the infusion procedure. [REDACTED]

[REDACTED]

[REDACTED]

[REDACTED]

[REDACTED]

[REDACTED]

[REDACTED]

[REDACTED]

For the subjects in cohort 1A the arterial and venous sheaths will be placed and procedure will continue as described above. For the subjects in cohorts 1B and 2—both limbs—the vascular sheaths will be placed on both sides (left and right) and the the subject will be anticoagulated and the occlusive balloon catheters positioned one side and the subject dosed. Upon completion of dosing of the first extremity, the other will be done. Three cohorts will undergo gene transfer in a dose escalation scheme to establish maximum tolerated dose (MTD) using toxicity. Cohort 1A (n=1) will receive a vector dose of 1×10^{12} vg/kg in a single lower extremity. In Cohort 1B (n=3), three subjects will receive the same vector dose per limb delivered bilaterally to both lower extremities for a total dose of 2×10^{12} vg/kg. This will be a one-time vector infusion as described above. Subjects in Cohort 2 (n=3) will receive 3×10^{12} vg/kg vector dose per extremity (6×10^{12} vg/kg total dose) delivered according to the identical protocol.

[REDACTED]

[REDACTED]

[REDACTED]

[REDACTED]

[REDACTED]

[REDACTED]

[REDACTED]

[REDACTED]

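### The section 7.3 dose table has no entry for the single-limb Cohort 1A, and its only Cohort (1) row gives two-limb totals that do not match the Cohort 1A dose in sections 6.3 and 7.2

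*Protocol*

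**What the plan says.** The text of the protocol is consistent about Cohort 1A.

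- Section 7.2: "This first subject will receive a perfusion to a single lower extremity with a total dose of 1×10^{12} vg/kg". The same paragraph gives Cohort 1B a total of 2e12 vg/kg over two limbs.
- Section 6.3: Cohort 1A receives 1e12 vg/kg "in a single lower extremity", and Cohort 1B the same dose per limb in both legs.
- Section 7.3, in the paragraph above the table: "the first patient (Cohort 1A) enrolled will receive a single unilateral infusion to one lower extremity".
- The protocol synopsis and SAP sections 2.2 and 2.3 also give 1A a single limb.

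The table in section 7.3 has two rows for three cohorts. Row (1) is labelled "LD 1e12vg/kg/limb" and row (2) "HD 3e12vg/kg/limb". The cells are headed, and the table captioned, as total vector genomes per patient or subject, indexed by 10-kg weight bands from 20-29 to 120-129 kg. The only footnote explains the abbreviations LD and HD. Nothing limits row (1) to Cohort 1B or says that it must be halved for one limb. The column holding the row labels is headed Dose/quad, although the labels are per limb and delivery is to the whole limb.

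**The concern.** A reader looking up the total for the first subject finds only one low-dose row. The synopsis groups 1A and 1B together as the low dose, so row (1) naturally reads as covering both. Its totals, however, are for two limbs.

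Section 3.0 records that the FDA asked for the first subject to be non-ambulatory and to receive vector in one limb only, to assess safety. The synopsis, section 7.2 and SAP section 2.3 then make Cohort 1B conditional on satisfactory safety in 1A. If a total were taken from the table and given to one limb, that step would not be run at the dose the text states, and the 1A safety data would describe a different per-limb exposure from the one used to open 1B.

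**Working it through.** **Inputs.** Per-limb doses of 1e12 and 3e12 vg/kg (row labels, section 7.3). Number of limbs: 1 for Cohort 1A, 2 for Cohorts 1B and 2 (sections 6.3 and 7.2). Cohort 1A total of 1e12 vg/kg (section 7.2). Weight rounded to the closest 5 kg, at the investigator's discretion (section 7.3).

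**Step 1: reproduce the table.** Total vg = dose per limb × limbs × weight. With 2 limbs and the lower edge of each band:

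- Low dose: 1e12 × 2 × 20 = 4e13, up to 1e12 × 2 × 120 = 2.4e14. All 11 cells match.
- High dose: 3e12 × 2 × 20 = 1.2e14, up to 3e12 × 2 × 120 = 7.2e14. All 11 cells match.

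Since all 22 cells follow one rule, damage from PDF extraction is not an explanation.

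**Step 2: test a one-limb reading.** With one limb, 4e13 vg at 1e12 vg/kg would need a weight of 40 kg, but the band is 20-29 kg. In every band the weight needed is twice the lower edge (40 to 240 kg), which lies outside the band. No low-dose cell can be a one-limb total.

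**Step 3: compare row (1) with the Cohort 1A dose in the text.** The ratio is the printed total ÷ (1e12 × weight). The same weight is used on both sides.

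| Band (kg) | Printed row (1), vg | One limb at band floor, vg | Ratio at floor | Ratio at top of band | Ratio at top, weight rounded to 5 kg |
|---|---|---|---|---|---|
| 20-29 | 4e13 | 2e13 | 2.00 | 1.38 | 1.33 |
| 30-39 | 6e13 | 3e13 | 2.00 | 1.54 | 1.50 |
| 40-49 | 8e13 | 4e13 | 2.00 | 1.63 | 1.60 |
| 50-59 | 1.0e14 | 5e13 | 2.00 | 1.69 | 1.67 |
| 60-69 | 1.2e14 | 6e13 | 2.00 | 1.74 | 1.71 |
| 70-79 | 1.4e14 | 7e13 | 2.00 | 1.77 | 1.75 |
| 80-89 | 1.6e14 | 8e13 | 2.00 | 1.80 | 1.78 |
| 90-99 | 1.8e14 | 9e13 | 2.00 | 1.82 | 1.80 |
| 100-109 | 2.0e14 | 1.0e14 | 2.00 | 1.83 | 1.82 |
| 110-119 | 2.2e14 | 1.1e14 | 2.00 | 1.85 | 1.83 |
| 120-129 | 2.4e14 | 1.2e14 | 2.00 | 1.86 | 1.85 |

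The last column finds the band from the actual weight and rounds the weight only for the text dose. For example, 49 kg falls in 40-49 and rounds to 50 kg, so 8e13 ÷ 5e13 = 1.60. If the rounded weight also selected the band, only weights at the floor and 5 kg above it would occur. The smallest ratio would then be 4e13 ÷ 2.5e13 = 1.60 at 25 kg, or 8e13 ÷ 4.5e13 = 1.78 from 40 kg up. The maximum is 2.00 either way.

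**Step 4: what the ratio means per limb.** At 70 kg the table prints 1.4e14 vg, and the text gives 1e12 × 70 = 7e13 vg. Placed in one limb, the printed total is 1.4e14 ÷ 70 = 2e12 vg/kg. That equals the stated Cohort 1B total for both limbs together, and is 2e12 ÷ 3e12 = two-thirds of the Cohort 2 per-limb dose.

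**The case against.** The strongest reply is that the table contains no arithmetic error. Every cell follows from its inputs, the row label is per limb, and the paragraph directly above says that 1A is unilateral. A careful reader would halve the cell. That stands as far as it goes: this is an inconsistency between a table and the text, not a miscalculation. It does not cure a table of totals per patient whose only Cohort (1) row does not fit one of the two Cohort 1 groups.

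A second reply is that the table may not be the working dosing document. It is captioned as a reference table, and 10-kg bands cannot carry out the 5-kg rounding rule. Section 6.3 says that the research pharmacist prepares the vector under the Manual of Operating Procedures, which is not available here, and parts of the procedure text are redacted. This also stands, and makes the consequence conditional. Against it, section 7.3 itself says that the table shows the dosing for the trial.

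Two stronger readings are tempting. A reader might infer that the first subject was assigned or given a double dose. The documents do not support that: every textual statement gives 1A one limb, and no administered dose is reported. A reader might also infer that a planned comparison of 1A with 1B is spoiled. No formal comparison is planned. The cohorts have one and three subjects, and the SAP gives descriptive summaries by cohort. Only the sequential safety step is at stake.

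Finally, the table edit may come too late for the 1A subject. Section 11.3.2.11 mentions cases already seen in subjects within this study, so dosing appears to have begun, and 1A was to be first. This limits the value of the edit but makes the exposure report more useful.

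**Conclusion.** The point holds as an internal inconsistency that should be corrected. The section 7.3 table has no Cohort 1A entry, and its only low-dose row gives two-limb totals. Read for 1A, that row is 2.0 times the total in section 7.2 at every band floor. With closest-5-kg rounding it is 1.33 to 2.0 times across the table, or 1.6 to 2.0 over 40-129 kg. The narrower range assumes an adult of at least 40 kg; the protocol requires 1A to be adult but gives no weight.

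The ratios assume the same weight on both sides. Section 7.2 refers to ideal weight for height and the table caption to body weight. A difference between those would change the ratio, but not the conflict over the number of limbs.

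The effect on the trial is conditional on a total having been taken from the table. This review does not say which dose is right, only that the places disagree and must be reconciled.

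**What to change.** - Reconcile the section 7.3 table with sections 6.3 and 7.2. Show Cohorts 1A and 1B separately, stating for each the number of limbs, the vg per limb and the total vg per subject.
- Reconcile the Dose/quad header with the per-limb row labels.
- Because dosing appears to have begun, report the vg actually given to the Cohort 1A subject next to the protocol-stated dose in the SAP section 6.6.1 exposure listing. That section already lists all recorded exposure data, so only the comparison is new.

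The cost is one added table row, some labels and one extra item in a planned listing, plus a check that the Manual of Operating Procedures agrees with the reconciled table. None of this needs new data collection if the administered vg are recorded in the eCRF.

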2.0 ABSTRACT

The proposed clinical trial is a dose escalation study of self-complementary scAAVrh74.tMCK.hSGCA vector and transgene to LGMD2D (alpha-SG deficient) subjects delivered via a major lower limb artery of each leg sequentially by isolated limb infusion (ILI)¹. Three cohorts (Cohorts 1A, 1B, and 2) will undergo gene transfer in a standard three-six dose escalation scheme to establish maximum tolerated dose (MTD) using toxicity. One (n=1) adult wheelchair-dependent patient will be enrolled in Cohort 1A, three (n =3) subjects will be enrolled in Cohort 1B, and three (n =3) subjects will be enrolled in Cohort 2. The first cohort (1A) will receive a vector dose of 1×10^{12} vg/kg (optimized weight to height) in a single limb with delivery to the whole limb. This same dose will be delivered to both limbs in Cohort 1B. Cohort 2 will receive a total dose of 3×10^{12} vg/kg per limb delivered to both lower extremities. The vector will be infused into an indwelling vascular sheath placed in the femoral artery. This will be a one-time vector infusion to an isolated limb with an approximately 10-minute dwell time. Cohort 2 will receive 6×10^{12} vg/kg total vector dose – split between the 2 lower extremities (3×10^{12} vg/kg per limb) delivered to the whole limb according to the same protocol. The total vector genome dose for each subject will be adjusted by rounding to the closest 5 kg (see section 6.2.7.3 Dose selection).

The primary objective of this study is the assessment of the safety of intravascular administration of scAAVrh.74.tMCK.hSGCA delivered via the femoral artery to lower extremities of LGMD2D (alpha-SG deficient) subjects. Safety monitoring during infusion will include: activated clotting times. Safety endpoints will be assessed by changes in hematology, serum chemistry, urinalysis, immunologic response to rAAVrh74 and hSGCA, and reported history and observations of symptoms.

The 6 minute walk test (6MWT) will be used as the secondary outcome for this study.

[REDACTED]

[REDACTED]

[REDACTED] These quantitative physical therapy measures will be done at baseline, day 60, 90, 180, month 9, 18 and at the end of 1st and 2nd years.

Subjects will be evaluated at baseline, infusion visit (days 0-1), and return for follow up visits on days 2, 7, 14, 30, 60, 90, and 180 and at months 9, 12, 18, and 24. [REDACTED]

[REDACTED]

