6.0 CLINICAL RESEARCH PLAN

6.1. STUDY POPULATION

Seven LGMD2D subjects with alpha-sarcoglycan deficiency by muscle biopsy or DNA testing, will be enrolled at Nationwide Children's Hospital for the gene transfer study. Subjects will encompass any ethnic, racial, or gender background. Patients must have proven muscle weakness to be enrolled.

6.2. PRE-TREATMENT ASSESSMENT:

A. Establish Subject Eligibility

I. Inclusion Criteria

1. Cohort 1A must be adult and wheelchair-dependent; Cohorts 1B and 2 will be subjects age 7 or older.
2. Confirmed alpha-sarcoglycan deficiency or identified SGCA DNA mutation.
3. Subjects enrolled in Cohorts 1B or 2 must be able to walk independently, but must exhibit signs of lower extremity weakness (i.e. a Gowers' sign, use a handrail for climbing stairs) and walk $\leq 80\%$ of predicted distance on the 6MWT based on normative data.
4. Males and females of any ethnic group will be eligible.
5. Ability to cooperate with muscle testing.
6. Willingness of sexually active subjects with reproductive capacity to practice reliable method of contraception (if appropriate), during the first six months after gene therapy (females) or until two negative sperm samples are obtained post gene transfer (males).

II. Exclusion Criteria

1. Active viral infection based on clinical observations.

2. The presence of SGCA mutations without weakness or loss of function.
3. Symptoms or signs of cardiomyopathy, including:
 - Dyspnea on exertion, pedal edema, shortness of breath upon lying flat, or rales at the base of the lungs.
 - Echocardiogram with ejection fraction below 40%.
4. Serological evidence of HIV infection, or Hepatitis B or C infection.
5. Diagnosis of (or ongoing treatment for) an autoimmune disease.
6. Abnormal laboratory values considered clinically significant (GGT > 3XULN, bilirubin \geq 3.0 mg/dL, creatinine \geq 1.8 mg/dL, Hgb < 8 or > 18 g/Dl; WBC > 15,000 per cmm).
7. Concomitant illness or requirement for chronic drug treatment that in the opinion of the PI creates unnecessary risks for gene transfer.
8. Pregnancy.
9. Subjects with AAVrh74 or AAV8 binding antibody titers \geq 1:50 as determined by ELISA immunoassay.

B. Informed Consent

Legally effective and properly executed written informed consent, in compliance with 21 CFR 50 and the International Conference on Harmonization (ICH) guidelines, will be obtained from

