In an attempt to dampen the host immune response to our AAV-based therapy, subjects will be started on a prophylactic daily dose of prednisone (or alternative glucocorticoid in dose equivalency) at approximately 1mg/kg/day with a maximum dose of 60 mg/day. Post-treatment, we may increase this dose to approximately 2 mg/kg/day with a maximum dose of 60 mg/day, depending on T cell responses measured by ELISpot assay. Treatment will be initiated one day prior to the gene transfer and the subjects will remain on prednisone treatment for approximately one month. A tapering protocol for prednisone will be implemented based on individual subjects' immune response to the gene transfer, again assessed by the ELISpot assay. If GGT elevations are seen after 30 days; the prednisone treatment will be continued or restarted at an appropriate dose for duration necessary to quell the immune reaction with a maximum of 60 mg per day. The duration of treatment will be determined based on weekly levels of GGT and immune responses.

Subjects will be admitted to the Nationwide Children's Hospital the day of the gene transfer. Procedures will be performed under sterile conditions in the Cardiac Catheterization Suite. An intravenous catheter with heparin lock will be placed in the arm for delivery of sedation.

I. Injection Preparation

Preparation of the scAAVrh74.tMCK.hSGCA gene vector will be done by the Nationwide Children's Hospital research pharmacist according to the Manual of Operating Procedures

(MOOP). Immediately prior to transportation to the clinical setting, appropriate dilutions of the test article will be completed by the pharmacy. [REDACTED]

[REDACTED]

[REDACTED]

Documentation of the dilution will be completed by the pharmacy following standard pharmacy protocol.

The vector-containing syringes will be delivered to the designated Cardiac Catheterization Suite at Nationwide Children's Hospital. It will be delivered under ambient temperature (not frozen) and administered to the subject within 8 hours of preparation. Handling of scAAVrh74.tMCK.hSGCA gene will follow compliance standards for Biosafety Level 1 vectors.

http://www4.od.nih.gov/oba/RAC/guidelines_02/APPENDIX_G.htm#_Toc7246561

II. Vector Administration Protocol

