11.6.3 PROPOSED DATES OF ENROLLMENT AND RECRUITMENT

We anticipate beginning enrollment in January 2014, with completion of enrollment December 2017. This protocol is listed in the Clinical Trials Data Bank of the NIH.

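### The dose table in protocol section 7.3 conflicts with the closest-5-kg rounding rule in the same section: every cell is the two-limb dose at the lowest weight of a 10-kg band

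*Protocol*

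**What the plan says.** Protocol section 7.3 gives a per-subject rule: "The total vector genomes dosed for each subject will be adjusted by rounding to the closest 5 kg per the discretion of the PI" or a designated co-investigator. Section 2.0 gives the same rule without the discretion clause and points to the dose section: the total "will be adjusted by rounding to the closest 5 kg (see section 6.2.7.3 Dose selection").

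Section 7.3 then presents a table: "Table 6.3 below shows dosing for the clinical trial based on weights from clinic subjects eligible for the clinical gene transfer trial". Its columns are eleven 10-kg bands, from 20–29 kg to 120–129 kg. It has one row for the low dose (1e12 vg/kg per limb) and one for the high dose (3e12 vg/kg per limb), with a single total per band. The caption reads "Reference Table: Total Dose (vg) per subject based on bodyweight (kg").

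The weight basis differs between places. Section 7.2 states the Cohort 1A dose as "vg/kg per limb (Ideal weight to height"), and section 2.0 uses an optimized weight to height for the same cohort. Cohort 1B gets the same dose per limb in both limbs.

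The vector is prepared by the "research pharmacist according to the Manual of Operating Procedures" (section 6.3). That manual is not among the documents, and text next to the preparation and cohort-dose passages in 6.3 is redacted.

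**The concern.** A rule that rounds weight to the closest 5 kg cannot produce one fixed dose for everyone from 20 to 29 kg. A reader who looks up a 27-kg child in the table finds 4e13 vg at the low dose; the rule gives 5e13.

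This matters because dose per kg defines the cohorts. The infusion is given once, and each bilateral cohort has three subjects, so one subject dosed off target is a third of that cohort's safety and walk-test data. The discrepancy is largest at low weights, and section 6.2 states that "Cohorts 1B and 2 will be subjects age 7 or older".

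**Working it through.** **Inputs (protocol 7.2 and 7.3).** Low dose 1e12 and high dose 3e12 vg/kg per limb; two limbs in Cohorts 1B and 2; the 22 table cells; rounding to the closest 5 kg.

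**Step 1: reproduce the table.** Cell = 2 limbs × dose per limb × lowest weight of the band.
- 20–29 kg, low dose: 2 × 1e12 × 20 = 4e13 (table 4e13).
- 20–29 kg, high dose: 2 × 3e12 × 20 = 1.2e14 (table 1.2e14).
- 120–129 kg, high dose: 2 × 3e12 × 120 = 7.2e14 (table 7.2e14).

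All 22 cells match exactly. For the first low-dose cell, other constructions fail: band midpoint (25 kg) gives 5e13, top of band (29 kg) 5.8e13, one limb at 20 kg 2e13.

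**Step 2: apply the rule to the same weights.** Let b be the lowest weight of a band. Whole weights ending in 0–2 round to b, those ending in 3–7 to b + 5, and those ending in 8–9 to b + 10. The table uses b throughout, so its shortfall against the rule is 0, 1 − b/(b + 5) or 1 − b/(b + 10).

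| Band (kg) | Ending 0–2 | Ending 3–7 | Ending 8–9 |
|---|---|---|---|
| 20–29 | 0 | 20.0% | 33.3% |
| 30–39 | 0 | 14.3% | 25.0% |
| 40–49 | 0 | 11.1% | 20.0% |
| 50–59 | 0 | 9.1% | 16.7% |
| 60–69 | 0 | 7.7% | 14.3% |
| 120–129 | 0 | 4.0% | 7.7% |

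Over the 110 whole weights from 20 to 129 kg, 11 × 3 = 33 agree and 11 × 7 = 77 are lower in the table. The shortfall is at least 10% at 31 weights, 21 of them below 50 kg.

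**Step 3: delivered dose as a share of nominal.**
- Table: lowest 20/29 = 0.69, highest 1.00. It is more than 10% below nominal at 28 of 110 weights, 22 of them among the 40 weights from 20 to 59 kg.
- Rule: lowest 20/22 = 0.91, highest 25/23 = 1.09. It is never more than 10% off.
- Example at 25 kg, per limb: table 4e13/2/25 = 0.80e12 (low) and 1.2e14/2/25 = 2.4e12 (high); rule 1.0e12 and 3.0e12.

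The cohorts stay apart: the lowest high dose under the table is 3e12 × 0.69 = 2.07e12, against a highest low dose under the rule of 1.09e12.

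**Step 4: relax the common weight basis.** Steps 2 and 3 enter the same weight in both. If the table is read with actual weight, as its caption suggests, and the rule with ideal weight, the sign can reverse. Hypothetical case: actual 60 kg, ideal 45 kg, low dose, both limbs. Table: 2 × 1e12 × 60 = 1.2e14. Rule: 2 × 1e12 × 45 = 9e13. The table is then 1.2e14/9e13 − 1 = 33% higher.

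**Step 5: row label.** The low-dose row is marked (1) but holds two-limb totals. Cohort 1A receives one limb, so its total at the same weight is half the entry.

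**The case against.** The best defence is that the table was never meant to set doses. The rounding sentence is an instruction for each subject and is repeated in section 2.0. The caption calls the table a reference table, its weights are said to come from clinic patients, and it has no single-limb row for Cohort 1A. Rounding is also left to the investigator's discretion. The redacted text or the pharmacy manual may state the calculation outright.

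Much of this stands. The visible wording does favour the rule, and it cannot be said that the plan lacks a governing statement, only that no visible text gives one. But the sentence introducing the table says that it shows the trial's dosing, and the columns are headed with weight ranges rather than example weights. Discretion over rounding to 5 kg does not turn a 29-kg subject into a 20-kg one.

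A second objection is that no enrolled weights are given, so the figures describe possible weights, equally spaced, not subjects. That is correct. From 60 kg upward the shortfall is at most 14.3%.

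A third is timing. Section 11.6.3 plans enrolment "with completion of enrollment December 2017", and the SAP is dated April 2022. Dosing may well be complete, in which case a new table changes no dose. That limits the practical benefit but does not make the text consistent.

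**Conclusion.** The conflict is real and certain as arithmetic: the table rounds weight down to 10 kg where the text rounds to the closest 5 kg. On a common weight basis the table is lower at 77 of 110 whole weights, by 4% to 33%, and equal at the other 33. It should be fixed, but no endpoint, analysis or escalation decision is shown to be affected.

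Three stronger readings are tempting and not supported:

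- **That the table can only under-dose.** This holds only if the same weight enters both. The documents name two weight bases, and in a subject whose actual weight is well above ideal weight the table could give more than the rule.
- **That subjects were misdosed.** Nothing shows that the table was used to dose anyone.
- **That Cohort 1A was given double.** The row label invites that misreading, but the row states its dose per limb and the text gives Cohort 1A a single-limb infusion.

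The percentages assume whole-kilogram weights between 20 and 129 kg and, except in step 4, one weight basis.

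**What to change.** In the protocol:

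- Re-issue the table in 5-kg steps from the stated rule, as two-limb totals (low / high): 20 kg 4e13 / 1.2e14; 25 kg 5e13 / 1.5e14; 30 kg 6e13 / 1.8e14; 35 kg 7e13 / 2.1e14; and so on. Alternatively, add one sentence that the 5-kg rule governs over the table.
- State one weight basis, ideal or optimized, for both text and table, and say that it applies to all cohorts.
- Label the low-dose row as Cohort 1B two-limb totals and note that Cohort 1A receives half.

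The cost is one table and caption, or one sentence plus the labels.

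If dosing is complete, an optional addition to the exposure listing in SAP 6.6.1 would show delivered vg/kg per limb (total vg ÷ limbs treated ÷ dosing weight) beside nominal. Listings are already by subject, so this is one derived column. It needs no new data if total vg and dosing weight are in the eCRF, which is an assumption.
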